11.2 Secondary Efficacy Variables

11.2.1 Sleep and Nap Diary

11.2.1.1 Sleep Latency

Sleep latency as assessed by a Sleep and Nap Diary will be calculated as the mean of the last 14 days prior to each scheduled visit. If the time the child went to bed and the time they woke up in the morning are the same, the sleep latency for that night will be set to 360 minutes. Mean sleep latency and the change from baseline in mean sleep latency will be summarized by scheduled visit using descriptive statistics. The change from baseline in sleep latency will be plotted over time. The change from baseline in mean sleep latency at 13 weeks will be analysed as detailed above for TST.

11.2.1.2 Duration of Wake

Duration of wake after sleep onset period as assessed by a Sleep and Nap Diary will be calculated as the mean of the last 14 days prior to each scheduled visit. Mean duration of wake and the change from baseline in mean duration of wake will be summarized by scheduled visit using descriptive statistics. The change from baseline in duration of wake will be plotted over time. The change from baseline in mean duration of wake at 13 weeks will be analysed as detailed above for TST.

11.2.1.3 Number of Awakenings

The number of awakenings as assessed by a Sleep and Nap Diary will be calculated as the mean of the last 14 days prior to each scheduled visit. The mean number of awakenings and change from baseline in the mean number of awakenings will be summarized by scheduled visit using descriptive statistics. The change from baseline in number of awakenings will be plotted over time. The change from baseline in the mean number of awakenings at 13 weeks will be analysed as detailed above for TST.

11.2.1.4 Longest Sleep Period

The longest sleep period as assessed by a Sleep and Nap Diary will be calculated as the mean of the last 14 days prior to each scheduled visit. The mean longest sleep period and the change from baseline in the mean longest sleep period will be summarized by scheduled visit using descriptive statistics. The change from baseline in longest sleep period will be plotted over time. The change from baseline in the mean longest sleep period at 13 weeks will be analysed as detailed above for TST.

11.2.1.5 Total Time in Bed

In order to evaluate the impact of shortening latency time versus increasing sleep time after sleep onset on the primary endpoint, TST, a new parameter will be further analysed by removing sleep latency from the TST calculation. This will be referred to as the total time in bed.

That is, total time in bed is defined as follows:

the time the child woke up in the morning *minus*

the time the child went to bed *minus*

the total duration of any night awakenings

The total time in bed as assessed by a Sleep and Nap Diary will be calculated as the mean of the last 14 days prior to each scheduled visit.

The mean total time in bed and the change from baseline in the mean total time in bed will be summarized by scheduled visit using descriptive statistics. The change from baseline in total time in bed will be plotted over time. The change from baseline in the mean total time in bed at 13 weeks will be analysed as detailed above for TST.

11.2.2 CSDI

Sleep disturbance as assessed by the CSDI and change from baseline will be summarized by scheduled visit for each treatment group using descriptive statistics for the total score. The change from baseline in the total CSDI score at 13 weeks will be analysed as detailed above for TST.

11.2.3 CGAS

The CGAS score and change from baseline will be summarized by scheduled visit for each treatment group using descriptive statistics. The change from baseline in CGAS score at 13 weeks will be analysed as detailed above for TST.

11.2.4 SDQ

The SDQ consists of 25 items which are divided into 5 subscales:

- 1) emotional symptoms (5 items)
- 2) conduct problems (5 items)
- 3) hyperactivity/inattention (5 items)
- 4) peer relationship problems (5 items)
- 5) prosocial behaviour (5 items).

Subscales 1 to 4 added together generate a total difficulties score (20 items). An impact score will also be calculated as part of the SDQ.

The following website provides SAS syntax to enable scoring of the 5 subscales: <http://www.sdqinfo.com/c2.html>. (Appendix A)

The total difficulties score, impact score and the subscale total scores and corresponding changes from baseline will be summarized by scheduled visit for each treatment group using descriptive statistics. The change from baseline in the scores at 13 weeks will also be analysed as detailed above for TST.

11.2.5 Number of Dropouts

The proportion of subjects dropping out in the double-blind phase will be compared between the treatment groups using a chi-square test with continuity correction.

Example SAS code for this analysis is given below:

```
proc freq data=drop;
  table drop*trtp/chisq;
  ods output chisq=chi(wher=(statistic='Continuity Adj. Chi-Square'));
run;
```

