The longest sleep episode will be assessed by a Sleep and Nap Diary, and will be summarized after 13 weeks (mean of the last 14 days before visit) of double-blind treatment (actual change from baseline) for each treatment group using descriptive statistics (n, mean, SD, median, minimum, and maximum). For each treatment group for this outcome, the mean score at 13 weeks will be compared, adjusting for baseline, using an ANCOVA model to test the null hypothesis so that these adjusted mean scores are equal.

The CGAS score will be summarized at baseline and after 13 weeks of double-blind treatment (actual change from baseline) for each treatment group using descriptive statistics (n, mean, SD, median, minimum, and maximum). For each treatment group for this outcome, the mean score at 13 weeks will be compared, adjusting for baseline, using an ANCOVA model to test the null hypothesis so that these adjusted mean scores are equal.

The SDQ score will be summarized at baseline and after 13 weeks of double-blind treatment (actual change from baseline) for each treatment group using descriptive statistics (n, mean, SD, median,

minimum, and maximum). For each treatment group for this outcome, the mean score at 13 weeks will be compared, adjusting for baseline, using an ANCOVA model to test the null hypothesis so that these adjusted mean scores are equal.

The number of dropouts will be compared between the treatment groups and analyzed using a dichotomized data analysis (chi-square test).

Sleep parameters, as measured by actigraphy, will be summarized at baseline and after 13 weeks of double-blind treatment (actual change from baseline) for each treatment group using descriptive statistics (n, mean, SD, median, minimum, and maximum). For each treatment group for this outcome, the mean score at each time point will be compared using an ANCOVA model to test the null hypothesis so that these mean scores are equal.

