8.3 Safety Set

Safety analyses will be performed on the Safety Analysis Set, which includes all subjects randomized to treatment who take at least one dose of study medication. Subjects will be classified according to actual treatment received. This analysis set will be used for all safety analyses.

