8.4 Full Analysis Set

Efficacy analyses will be performed on the Full Analysis Subset (FAS), and will include all subjects in the Safety Analysis Set who satisfy all major entry criteria (Inclusion Criteria 1-5) and who have a valid mean TST result recorded for baseline and at least one post-baseline period assessment during the double blind phase. Subjects will be classified according to randomized treatment. This analysis set will be used for all efficacy analyses.

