10.6 Prior and Concomitant Medications

Concomitant medications recorded during the study will be coded using World Health Organization (WHO)-Drug. Details of concomitant medication will be listed.

Concomitant medications will be summarized according to whether they were being taken pre-study (prior medications) and/or during the study (concomitant medication). Prior medications are any that were being taken prior to the first dose of study medication (medication stop date prior to the first dose of study medication). Concomitant medications are any that were being taken on or after the first dose of study medication. If the start and stop dates of the concomitant medications do not clearly define the period during which a medication was taken, it will be assumed to be a concomitant medication.

Concomitant medications will be assigned to the phase they were taken: Double-Blind, first Open-Label, second Open-Label. If a concomitant medication starts or is ongoing between Visit 2 and Visit 4, it will be assigned to the Double-Blind phase. If a concomitant medication starts or is ongoing between Visit 4 + 1 day and Visit 5, it will be assigned to the first Open-Label phase. If a concomitant medication starts or is ongoing between Visit 5 + 1 day and Visit 8, it will be assigned to the second Open-Label phase. If the start and stop dates of the concomitant medications do not clearly define the phase during which a medication was taken, it will be assumed to be taken across all phases.

Prior and concomitant medications will be summarized by Anatomical Therapeutic Chemical (ATC) level 2 term and preferred term.

Details of non-pharmacological concomitant measures will be listed.

11 Efficacy

Subjects will be classified and summarized by randomized treatment. For all efficacy assessments, the baseline values will be calculated as the last recorded value prior to the start of randomized treatment. Change from baseline values will be calculated as the assessment score minus the baseline value. For questionnaires the change from baseline values will be calculated for each item and total/subscale score as applicable.

All summaries and analyses will be performed on the FAS set. The primary efficacy endpoint and select secondary efficacy endpoints will also be analyzed on the PP set. Analyses looking at the impact missing data on the primary efficacy endpoint will also be performed on the All Randomized set.

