11.1 Primary Efficacy Variable

11.1.1 Total Sleep Time (TST)

TST will be assessed by a Sleep and Nap Diary.

Daily TST will be calculated programmatically as follows:

the time the child woke up in the morning *minus*

the time the child went to bed *minus*

the time taken to fall asleep *minus*

the total duration of any night awakenings

If the time the child went to bed and the time they woke up in the morning are the same, the TST will be set to 0.

The number of daily diaries with data recorded and the number of daily diaries with a valid mean TST will be tabulated by scheduled visit.

For each subject the mean TST will then be calculated as the mean of the last 14 days prior to each scheduled visit. A subject will be required to have a minimum of 3 nightly TST values per week (6 nights in total) in order to have a valid mean TST after baseline. A subject will be required to have a minimum of 6

nightly TST values across the 2 weeks in order to have a valid mean TST at baseline. The mean TST and change from baseline in mean TST will be summarized by scheduled visit using descriptive statistics. The change from baseline in mean TST will be plotted over time. Empirical cumulative distribution functions by treatment group will be plotted for change from baseline in mean TST at Visit 4 (Week 15).

The change from baseline in mean TST will be analyzed using a mixed-effects model for repeated-measures (MMRM). The model will contain the TST at Visit 3 (Week 5) and Visit 4 (Week 15) as the dependent variable, with fixed effects for visit, the mean baseline TST, randomized treatment and the mean baseline TST and randomised treatment both nested within visit. Visit-to-visit repeated measures will assume a general (unstructured) covariance structure. Standard errors and degrees of freedom for significance tests will be derived using the Kenward-Roger method [1].

From this model, the adjusted mean change from baseline (and standard error) in TST after 13 weeks of treatment for each treatment group will be calculated and the associated 95% confidence intervals (CI) for the change presented. Furthermore, the estimated difference (and standard error) between treatments will be estimated, the associated 95% CI presented and the null hypothesis that these means are equal will be tested.

Example SAS code for this analysis is given below:

```
proc mixed data=tst method=reml;
  class subjid trtp avisitn;

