Table 14.2.17.4	SDQ Total Difficulties Score Change from Baseline at 13 Weeks Double Blind – MMRM Analysis including Prior Clonidine Use as a Factor	FAS Set
Table 14.2.18.1	SND Total Sleep Time and Change from Baseline – Double Blind - Descriptive Statistics by Final Dose	FAS Set
Table 14.2.18.2	SND Sleep Latency and Change from Baseline – Double Blind - Descriptive Statistics by Final Dose	FAS Set
Table 14.2.18.3	SND Duration of Wake and Change from Baseline – Double Blind - Descriptive Statistics by Final Dose	FAS Set
Table 14.2.18.4	SND Number of Awakenings and Change from Baseline – Double Blind - Descriptive Statistics by Final Dose	FAS Set
Table 14.2.18.5	SND Longest Sleep Period and Change from Baseline – Double Blind - Descriptive Statistics by Final Dose	FAS Set
Table 14.2.18.6	SND Total Sleep Time and Change from Baseline – Open Label - Descriptive Statistics by Final Dose	FAS Set
Table 14.2.18.7	SND Sleep Latency and Change from Baseline – Open Label - Descriptive Statistics by Final Dose	FAS Set
Table 14.2.18.8	SND Duration of Wake and Change from Baseline – Open Label - Descriptive Statistics by Final Dose	FAS Set
Table 14.2.18.9	SND Number of Awakenings and Change from Baseline – Open Label - Descriptive Statistics by Final Dose	FAS Set
Table 14.2.18.10	SND Longest Sleep Period and Change from Baseline – Open Label - Descriptive Statistics by Final Dose	FAS Set
Table 14.2.19	Summary of Level of Agreement between Sleep and Nap Diary and Actigraphy Assessment of Responder	FAS Set
Table 14.3.1.1	Summary of Study Drug Exposure	Safety Set
Table 14.3.1.2	Summary of Study Drug Modifications	Safety Set
Table 14.3.1.3	% Compliance by Scheduled Visit	Safety Set
Table 14.3.1.4	Dosage Achieved by Scheduled Visit	Safety Set
Table 14.3.1.5	Number of Dropouts -Chi-Square Test	Safety Set
Table 14.3.2.1	Summary of TESS by Scheduled Visit	Safety Set

Table Number	Table Title	Population
Table 14.3.2.2	Overall Adverse Event Summary: Double Blind Phase	Safety Set
Table 14.3.2.3	Overall Adverse Event Summary: Open Label Phase	Safety Set
Table 14.3.2.4	Treatment Emergent Adverse Events by System Organ Class and Preferred Term: Double Blind Phase	Safety Set
Table 14.3.2.5	Treatment Emergent Adverse Events by System Organ Class and Preferred Term: Open Label Phase	Safety Set
Table 14.3.2.6	Serious Adverse Events by System Organ Class and Preferred Term: Double Blind Phase	Safety Set

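### The SAP assigns the dropout comparison to two different populations, and one of them, the FAS, leaves out children who drop out before giving a valid diary mean

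*SAP*

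**What the plan says.** Protocol 5.2 and SAP 4.2 both list the number of dropouts over the 13-week double-blind period as a secondary endpoint. The plan for testing it is spread over several places.

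- **Test.** Protocol 12.8.1 says the number will be "analyzed using a dichotomized data analysis (chi-square test"). SAP 11.2.5 says the proportion "will be compared between the treatment groups using a chi-square test with continuity correction", and its example code keeps only the row labelled "Continuity Adj. Chi-Square". SAP section 14, on changes to planned methodology, lists only the move of the CSDI score.
- **Population, by text.** SAP 11.2.5 names none. It sits among the secondary efficacy variables, and the opening of section 11 states: "All summaries and analyses will be performed on the FAS set". SAP 8.4 likewise assigns all efficacy analyses to the FAS, by randomised treatment.
- **Population, by table list.** SAP 16.1 lists Table 14.3.1.5, "Number of Dropouts -Chi-Square Test", on the Safety Set. SAP 8.3 classifies that set by actual treatment received.
- **Membership.** The FAS needs a valid mean TST at baseline and "at least one post-baseline period assessment during the double blind phase". SAP 11.1.1 defines a valid post-baseline mean by a "minimum of 3 nightly TST values per week (6 nights in total"). The Safety Set takes "all subjects randomized to treatment who take at least one dose of study medication".

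SAP 8.2 also defines an All Randomized Set, by randomised treatment. It is not assigned to this test.

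**The concern.** Two programmers could each follow the SAP and produce different denominators, different arm assignments and different p-values for one prespecified secondary endpoint. Nothing in the SAP says which instruction prevails.

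The two candidates are not equally harmless. FAS membership depends on having stayed long enough to give a valid diary mean, so the FAS filters on the event being counted. Dropout also bears on tolerability, and early leavers are informative for that purpose. Losing them unequally between arms would distort the comparison.

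The continuity correction is a separate and smaller matter. It makes the test less sensitive to a real imbalance, and the SAP does not record it as an addition to the protocol.

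**Working it through.** **Figures in the plan.** Neither document gives an expected double-blind dropout rate, or any power or error figure for this test. The nearest figures are in SAP 6.2: 120 randomised 1:1 (60 per arm), with at least 90 completing to Week 28. That is (120 − 90)/120 = 25%. It covers the double-blind phase and the first open-label period together, so it is a planning ceiling for the double-blind phase alone.

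**Who the FAS removes.** The first post-baseline diary mean is at Visit 3, after 3 weeks of treatment, and uses the preceding 14 days. Three nights are needed in each of those two weeks. Visit windows aside, a child who leaves in the first two weeks cannot qualify. A later leaver with too few diary nights does not qualify either.

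**Effect on the observed rate.** Let D be the dropouts, N the number randomised and E the dropouts with no valid post-baseline mean. The true rate is D/N and the FAS rate is (D − E)/(N − E). Take D = 30 and N = 120, with the early fraction assumed and no other exclusions:

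| Early fraction | E | FAS rate | All randomised |
|---|---|---|---|
| 20% | 6 | 24/114 = 21.1% | 25% |
| 33% | 10 | 20/110 = 18.2% | 25% |
| 50% | 15 | 15/105 = 14.3% | 25% |

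**Effect on the comparison.** This depends on how early dropout splits by arm. With 9/60 against 21/60, the corrected test gives p = 0.020. If 3 early dropouts in the worse arm fall outside the set, 9/60 against 18/57 gives p = 0.056.

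**Effect of the Safety Set.** Only never-dosed children can be lost. From 18/60 against 12/60 (a difference of 10.0 points), removing one undosed dropout per arm gives 17/59 = 28.8% against 11/59 = 18.6%, a difference of 10.2 points.

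**Continuity correction.** For a 2×2 table with cells a, b, c, d and total N:

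- Pearson: N(ad − bc)² / (product of the four margins)
- Corrected: N(max(0, |ad − bc| − N/2))² / (same product)

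Take 20/60 against 10/60. Then |ad − bc| = 20×50 − 40×10 = 600, and the product of margins is 60×60×30×90 = 9,720,000. Pearson is 120×600²/9,720,000 = 4.44 (p = 0.035). Corrected is 120×540²/9,720,000 = 3.60 (p = 0.058).

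Exact binomial enumeration of all tables at 60 per arm, rejecting above 3.841 (two-sided 5% assumed, since the SAP states the level only for the primary objective):

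| Common dropout rate (assumed) | Size, uncorrected | Size, corrected |
|---|---|---|
| 10% | 5.05% | 2.18% |
| 15% | 4.69% | 2.66% |
| 20% | 4.99% | 2.82% |
| 25% | 5.22% | 2.96% |

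Power for 10% against 25% is 58.5% uncorrected and 49.4% corrected.

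**The case against.** Three stronger readings are tempting. The documents do not support them.

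**Both sets lose randomised dropouts.** This is not established for the Safety Set. Protocol 8.17 calls the run-out placebo study medication, and Protocol 8.3 describes the product dispensed at Visit 1, before the placebo run-in, as study drug. SAP 9.3 uses a distinct phrase when it means treatment after randomisation. If a run-in dose counts, the Safety Set may lose nobody. The documents leave this open, and even on the narrower reading the loss is probably small. The Safety Set label is also the only entry that names a population for this particular test, so it may be what was intended.

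**A true excess of dropout could be hidden or reversed.** A reversal can be constructed: 18/60 with 12 early against 12/60 with 4 early becomes 6/48 = 12.5% against 8/56 = 14.3% on the FAS. That split is chosen to produce the result, and nothing in the plan makes it likely. The FAS can also lose children who stayed but kept poor diaries, which pushes the observed rate the other way. The report would not conceal the discontinuations in any case. SAP 10.1 tabulates numbers randomised and completing double-blind treatment, with reasons for stopping, and Table 14.1.1.1 is on the All Enrolled Set. What is exposed is one comparison and its p-value.

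**The continuity correction is an error that halves the error rate.** A corrected chi-square is still a chi-square test, and Protocol 12.2 expects the SAP to add detail. The correction is prespecified and conservative, and statisticians differ on its use. The size of the reduction depends on an assumed rate: corrected size is 43% to 57% of uncorrected at 10% to 25% dropout, but 23% at 5% dropout and 63% at 40%. Neither version has high power for 10% against 25%.

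None of this removes the conflict between the section 11 text and the table list, or makes the FAS a sound denominator for counting dropouts.

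**Conclusion.** The SAP gives two incompatible populations and two arm-assignment rules for one secondary endpoint, and this should be resolved. The FAS is unsuitable because membership requires remaining until a valid diary mean exists. Its effect cannot be sized from the documents. The fall from 25% to between 21% and 14% assumes 30 dropouts among 120 and an early fraction of 20% to 50%, and the effect on the between-arm difference could go either way. The Safety Set is the lesser problem and may omit nobody.

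The correction is a secondary suggestion. At 60 per arm and an assumed 10% to 25% dropout, it lowers the test's size from 4.7–5.2% to 2.2–3.0% and costs about 9 points of power for 10% against 25%. It does not inflate the type I error.

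The primary TST analysis is not affected.

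**What to change.** In SAP 11.2.5 and in the population column for Table 14.3.1.5, specify the All Randomized Set, by randomised arm. Add an exemption for this test to the section 11 sentence on the FAS and to 8.4. Report the difference in dropout proportions with its 95% confidence interval beside the p-value.

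Optionally, either use the uncorrected Pearson chi-square, or keep the correction and record it in section 14 as a deliberate conservative choice. The code line that selects the statistic needs editing anyway, because its where option is misspelt.

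The cost is a few words of SAP text, one table-list entry and one or two lines of code. No data collection or trial conduct changes.

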11.2.6 Actigraphy

Sleep parameters (Total Sleep Time, Sleep Latency, Duration of Wake and Number of Awakenings, Longest Sleep Period and Sleep Efficiency) as measured by actigraphy will be calculated as the mean of the last 14 days prior to each scheduled visit. The sleep parameters and corresponding changes from baseline will be summarized by scheduled visit using descriptive statistics. The sleep parameters at 13 weeks will be analysed as detailed above for TST.

